#### Group III: potent

Amcinonide  
Beclometasone  
Betamethasone  
Betamethasone dipropionate  
Budesonide  
Desoximetasone  
Diflorasone  
Diflucortolone  
Fluclorolone acetonide  
Fludroxycortide  
Fluocinolone acetonide  
Fluocinonide  
Fluocortolone  
Fluticasone  
Halometasone  
Mometasone

Prednicarbate

Ulobetasol

**Group IV: very potent**

Clobetasol

Halcinonide

## 20 Appendix 8: WHO Classification of Topical Corticosteroids compared to the Japanese Classification

WHO Classification of Topical Corticosteroids	
Group I : Weak	Hydrocortisone Methylprednisolone Prednisolone
Group II : Moderately Potent	Alcometasone Clobetasone Desonide Flumetasone Fluocortin butyl Fluprednidene Hydrocortisone butyrate Triamcinolone

Japanese Classification of Topical Corticosteroids	
Group V : Weak	Dexamethasone Fludroxycortide Hydrocortisone acetate Prednisolone
Group IV : Medium	Alclometasone dipropionate Clobetasone butylate Flumetasone pivalate Hydrocortisone butyrate Triamcinolone acetate
Group III : Strong	Betamethasone valerate Beclometasone dipropionate Deprodone propionate Dexamethasone propionate Dexamethasone valerate Fluocinolone acetate Prednisolone valerate acetate

WHO Classification of Topical Corticosteroids	
Group III : Potent	Amcinonide Beclometasone Betamethasone Betamethasone dipropionate Budesonide Desoximetasone Diflorasone Diflucortolone Fluclorolone acetonide Fludroxycortide Fluocinolone acetonide Fluocinonide Fluocortolone Fluticasone Halometasone Mometasone Prednicarbate Ulobetasol
Group IV : Very Potent	Clobetasol Halcinonide

Japanese Classification of Topical Corticosteroids	
Group II : Very Strong	Amcinonide Betamethasone butyrate propionate Betamethasone dipropionate Diflucortolone valerate Difluprednate Fluocinonide Hydrocortisone butyrate propionate Halcinonide Mometasone fluorate
Group I : Strongest	Clobetasol propionate Diflorasone diacetate

## **21 Appendix 9: Descriptors for intermediate intervals in severity score of clinical signs of target lesion**

In the Investigator's assessment of the severity of clinical signs of the target lesion, intermediate intervals (0.5, 1.5, 2.5, 3.5) serve as mid-points between the defined grades (0, 1, 2, 3, 4). For the purposes of data coding, these intermediate levels are defined as:

0.5 = mid-point between 'none' and 'slight'

1.5 = mid-point between 'slight' and 'mild'

2.5 = mid-point between 'mild' and 'moderate'

3.5 = mid-point between 'moderate' and 'severe'

Signature Page for TMF-000095061 v1.0

Reason for signing: Approved	Manager Name: PPD Capacity: [REDACTED] Date of signature: 06-Nov-2018 09:12:05 GMT+0000
------------------------------	---

Reason for signing: Approved	Manager Name: PPD Capacity: [REDACTED] Date of signature: 06-Nov-2018 09:34:26 GMT+0000
------------------------------	---

Reason for signing: Approved	Manager Name: PPD Capacity: [REDACTED] Date of signature: 06-Nov-2018 11:23:34 GMT+0000
------------------------------	---

Electronic signatures made within eTMF LEO are considered to be a legally binding equivalent of traditional handwritten signatures.

3.1 List of Abbreviations

ATC	Anatomical Therapeutic Chemical
CPMP	Committee for Proprietary Medicinal Products
CRA	Clinical Research Associate
CRF	Case Report Form
CRO	Contract Research Organisation
CTP	Clinical Trial Protocol
GCP	Good Clinical Practice
ICH	International Conference on Harmonisation
IRB	Institutional Review Board
LOCF	Last observation carried forward
MedDRA	Medical Dictionary for Regulatory Activities
PPAS	Per protocol analysis set
SAP	Statistical Analysis Plan
SOC	System Organ Class
SOP	Standard Operating Procedure

4 Statistical Analysis Plan Authors

PPD [REDACTED], Statistical Analysis 1st Dept. Data Science Div., CMIC Co., Ltd., [name], Tel: PPD [REDACTED], Fax: +81 PPD [REDACTED], email: PPD [REDACTED]

PPD [REDACTED], Statistical Analysis 1st Dept. Data Science Div., CMIC Co., Ltd., [name], Tel: PPD [REDACTED], Fax: PPD [REDACTED], email: PPD [REDACTED]

PPD [REDACTED], Statistical Analysis 1st Dept. Data Science Div., CMIC Co., Ltd., [name], Tel: PPD [REDACTED], Fax: PPD [REDACTED], email: PPD [REDACTED]

5 Introduction

The statistical analysis will be performed as outlined in the Clinical Trial Protocol (CTP). This Statistical Analysis Plan, prepared before the end of the blinding period, contains a more technical and detailed elaboration of some points in the statistical analysis described in the CTP. Refer to the "Blinding Plan" as referenced in eTMF, document number TMF-000130194, for the blinding period. In addition, any changes to the analyses planned in the CTP are described.

Trial ID: LP0053-1422	Date: 21JUN2019	Version: 1.0 Page 8 of 26
-----------------------	-----------------	------------------------------

6 Statistical Analysis

6.1 Software and Dictionaries

The software and its versions used in this trial are listed below.

	Software and Versions
Operating System	Microsoft Windows 7
Statistical Analysis Software	SAS Ver.9.3 or later
Tabulation Software	Microsoft Word 2010

The coding items and dictionaries used in this trial are listed below.

Category	Dictionary	Remarks
Adverse Event, Concurrent Diagnoses Indications for concurrent medications Concurrent procedures and their indications	MedDRA [*] /J Version 21.1	Apply System Organ Class (SOC) and Preferred Term (PT) to Items listed opposite
Product Name (Concurrent Medication)	WHO Drug Version Sep 2018	

6.2 Protocol Deviations

Protocol deviations for all subjects will be presented in the listings.

Trial ID: LP0053-1422	Date: 21JUN2019	Version: 1.0 Page 9 of 26
-----------------------	-----------------	------------------------------

6.3 Subject Disposition

In addition to what is described in the CTP (section 6.1), date of first subject visit, date of last subject visit, and duration of trial period for each site and for all enrolled subjects will be provided. Also the number of subjects enrolled, the number of subjects randomised, and the number of subjects randomised to each treatment group will be presented by site.

The reason for leaving the trial will be presented as described in the CTP (section 11.3.1).

6.4 Demographics and other Baseline Considerations

The demographics and other baseline (screening visit) characteristics will be presented as described in the CTP (section 11.3.2).

Concurrent diagnoses (except Psoriasis Vulgaris) including indications for concomitant medication at screening for concurrent medications and concurrent procedures at screening visit. Concurrent diagnosis coded with the MedDRA preferred term of "psoriasis" will be excluded from the summary tables.

Concurrent medications started before screening visit will be presented, which are defined as those started before screening visit or marked as "before".

Similarly, concurrent medications started after screening visit will be presented in a separate table, which are defined as those started after screening visit or, marked as "after", or those started on or after the screening visit.

In addition to what is described in the CTP, the time interval (days) from visit 1 to each trial visit will be summarized for all randomised subjects and by treatment group.

6.5 Compliance

Compliance with treatment instructions will be presented as described in the CTP (section 11.3.3).

6.6 Analysis of Efficacy

6.6.1 Primary Efficacy Criteria

The primary endpoint will be analysed as described in the CTP (section 11.3.4).

In addition, the difference (LEO 90100 foam – Dovobet[®] ointment) in the proportion of subjects with overall improvement rate, its 95% confidence interval will also be presented. Refer to CTP (11.3.11) for the imputation method.

For subjects who completed the trial before 4 weeks of treatment due to achieving substantial resolution, use the latest available results for LOCF imputation. This approach of imputation is legitimate under the assumption of short exposure time and type of population included; a re-lapse on the disease in the target area will not be expected.

6.6.2 Secondary Efficacy Criteria

The secondary endpoints will be analysed as described in the CTP (section 11.3.5).

There are two different descriptions on total sign score in the CTP (Section 5.2):

- The change in the total sign score from Visit 1 to Visit 4; total sign score is defined as the sum of the scores from the 3 clinical signs assessing severity in the target lesion.
- The change in the sum of the scores (total sign score) for the severity of the three clinical signs (thickness, scaliness, redness) from Visit 1 to the sum of the scores at Visit 4 (end of Week 4) for the target lesion

Since these two endpoints are the identical endpoint, both of them will be regarded as "the change in the total sign score for the target lesion from baseline to Visit 4".

Total sign score is treated as missing when the score for at least one of the clinical signs is missing. LOCF will be used to impute any missing values for Visit 4 for the analysis of change in total sign score from baseline to Visit 4 (end of Week 4).

6.6.3 Exploratory Efficacy Criteria

The exploratory analysis of efficacy will be presented as described in the CTP (section 11.3.6).

In addition to what is stated in the CTP, the followings will also be analysed:

The treatment difference of the change in each clinical sign (thickness, scaliness and redness) at Visit 4 will be estimated with an ANOVA with treatment as fixed effect.

For the analysis of change in score for the severity of each clinical sign from baseline to Visit 4 (end of Week 4), LOCF will be used to impute any missing values for Visit 4.

6.6.4 Exploratory Efficacy Criteria of Subject Assessments

The subject assessments for "time spent for application" and "ease of application" will be presented as described in the CTP (section 11.3.7). The tabulations will be provided for the full analysis set.

The subject's assessment of "time spent for application" of trial medication will be compared between the treatment groups using ordinal logistic regression. The odds ratio (odds of being less time applying LEO 90100 foam group relative to Dovobet[®] ointment group), its 95% CI, and a p-value will be calculated from the logistic model.

The subject's assessment of "ease of application" of trial medication will be compared between the treatment groups using ordinal logistic regression. The odds ratio (odds of being very easy applying LEO 90100 foam group relative to Dovobet[®] ointment group), its 95% CI, and a p-value will be calculated from the logistic model.

This analysis will be performed using full analysis set.

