### **4.3 Exploratory Objectives**

To investigate the subjects' own assessments of the use of LEO 90100 foam compared to previous psoriasis treatments for non-naïve subjects.

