### 5.3 Exploratory Endpoints

The following will be analysed as exploratory efficacy endpoints.

- The ‘substantial resolution’ of clinical signs for the target lesion for each visit
- The change in the total sign score for the target lesion from Visit 1 to Visits 2 and 3 (end of Weeks 1 and 2)
- The change in score for the severity of each clinical sign for the target lesion from Visit 1 to each subsequent visit

For those subjects who have previously used topical treatment for their psoriasis, the following will be analysed as exploratory endpoints evaluating subject assessment on the use medication:

- ‘time spent for application’ compared to the previous treatment (less time, slightly less time, unchanged, slightly more time, more time) at Visit 4 (end of Week 4)
- ‘ease of application’ (very easy, easy, difficult, very difficult) at Visit 4 (end of Week 4)

Exposure and standard safety data will be analysed as described in sections [11.3.3](#) and [11.3.8](#).

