### 8.13 Subject's Assessments

At Visit 4, the subject will make the following assessments. If a subject withdraws from or completes the trial at Visits 2 or 3, the assessment should be done at this time in lieu of the one at Visit 4.

Time spent for application, scored as less time, slightly less time, unchanged, slightly more time, more time as compared to previous topical treatments.

Ease of application, scored as very easy, easy, difficult, very difficult as compared to previous topical treatments.

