### **11.3.7 Exploratory Analysis of Subject Assessments**

The number and percentage of subjects in each category for ‘time spent for application’ (less time, slightly less time, unchanged, slightly more time, more time) and ‘ease of application’ (very easy, easy, difficult, very difficult) will be tabulated at Visit 4 (end of Week 4) by treatment group.

In addition, a difference between the two treatment groups will be calculated for each subject assessment with odds ratio and 95% confidence interval.

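### The SAP analyses time spent and ease of application in the full analysis set without the protocol's restriction to previous users of topical treatment, and declares no change

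*SAP*

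**What the plan says.** Protocol 5.3 introduces the two assessments with a population: "For those subjects who have previously used topical treatment for their psoriasis, the following will be analysed as exploratory endpoints". The exploratory objective in protocol 4.3 is likewise to study the foam "compared to previous psoriasis treatments for non-naïve subjects".

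The protocol's analysis text does not repeat this. Section 11.3.7 says that the categories "will be tabulated at Visit 4 (end of Week 4) by treatment group", and plans an odds ratio with a 95% confidence interval for each assessment. It names neither an analysis set nor a subgroup.

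SAP 6.6.4 refers to 11.3.7, not to 5.3. For the tables it states: "The tabulations will be provided for the full analysis set". It then adds an ordinal logistic regression with a p-value for each assessment and closes: "This analysis will be performed using full analysis set". Tables E18 and E19 in SAP Appendix I carry the full analysis set label, and their titles keep the reference to previous topical treatment. Protocol 11.2 defines the full analysis set as all randomised subjects, apart from justified special exclusions.

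On data collection, protocol 8.13 says: "At Visit 4, the subject will make the following assessments". Both items are worded there as comparisons with earlier topical treatments, as they are in footnote f of the schedule in 8.1.

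**The concern.** The restriction in 5.3 is part of the endpoint definition. A subject who has never used a topical psoriasis treatment cannot say whether the trial product takes more or less time than the last one. An answer given anyway has no defined meaning, yet under SAP 6.6.4 as written it would count in the odds ratio, its interval and the p-value.

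The SAP's introduction undertakes to describe changes from the protocol, and protocol 11.3.10 requires them to be described and justified. None is described here, although SAP 6.6.2 does reconcile a different wording problem in protocol 5.2. Protocol 3.3 gives convenience and shorter application time as the reasons for developing the foam, so these results are likely to be quoted and their population should be unambiguous.

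**Working it through.** **1. Can naïve subjects reach the analysis as written?**

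| Step | Where | What it says |
|---|---|---|
| Entry | Protocol 7.2 | Disease must be amenable to topical treatment; previous use is not required |
| Question | Protocol 8.13, 8.1 footnote f | Put to the subject at Visit 4 or at early exit; no skip rule, no not-applicable category |
| Endpoint | Protocol 5.3 | Previous users of topical treatment only |
| Analysis | Protocol 11.3.7 | Restriction absent |
| Analysis set | SAP 6.6.4, E18, E19 | Full analysis set, no subset |

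Nothing between entry and model removes a naïve subject who records an answer.

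**2. What could it do to the estimate?** The documents give no figure to reproduce: no naïve share, no expected odds ratio, and a sample size not based on power (protocol 6.2). The following is a range under assumptions, for the five-category time item only.

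Inputs: 90 per group (protocol 6.2), everyone answering unless stated; the same naïve share in both arms, assumed at 10, 20 or 30%; an assumed ointment distribution of 15/20/40/15/10% from less time to more time; an assumed odds ratio of 2.0 in previous users.

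Ointment cumulative shares are 0.15, 0.35, 0.75, 0.90, with odds 0.176, 0.538, 3, 9. Doubling the odds and converting back by odds/(1 + odds) gives foam cumulative shares of 0.261, 0.519, 0.857, 0.947.

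With naïve share f, each arm's cumulative share is (1 − f) × previous users + f × naïve. Example: f = 0.30 and naïve answers distributed as in the ointment group in both arms.

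- Foam, first cut: 0.7 × 0.261 + 0.3 × 0.15 = 0.228, odds 0.295; ratio 0.295/0.176 = 1.67.
- Second to fourth cuts, same steps: 1.63, 1.57, 1.55.
- Proportional-odds maximum-likelihood fit to these expected counts: 1.62.

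Fitted odds ratio in the unrestricted set:

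| How naïve subjects answer | 10% | 20% | 30% |
|---|---|---|---|
| No difference between arms | 1.86 | 1.74 | 1.62 |
| Practically all unchanged | 1.93 | 1.87 | 1.82 |
| Same difference as previous users | 2.00 | 2.00 | 2.00 |
| Larger difference (odds ratio 4) | 2.14 | 2.28 | 2.44 |
| Item left blank | 2.00 | 2.00 | 2.00 |

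**3. What does restricting cost?** Per-group n falls to 90 × (1 − f) = 81, 72 or 63. The expected z (log odds ratio over its standard error) is then 2.41, 2.27 or 2.12, against 2.54 if all 90 were previous users. When naïve answers show no difference between arms, the unrestricted analysis has z of 2.29, 2.03 or 1.78. Restricting therefore loses precision only relative to the case in which naïve subjects behave like everyone else.

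**4. The ease item.** It has four categories and no unchanged option, so the second row of the table cannot apply to it. Protocol 5.3 lists the categories without a comparator, whereas 8.13 makes them relative to previous topical treatments. A naïve subject could answer the first form but not the second.

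**The case against.** The strongest defence is that full analysis set here names only the parent set, as opposed to the per protocol set. Protocol 8.13, footnote f and the titles of E18 and E19 all keep the comparison with previous topical treatment, so naïve subjects may simply have no record. The case report form is not among the documents, so this cannot be excluded. But a table title excludes nobody, and a programmer following 6.6.4 would use every recorded answer.

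It is also fair to say that the gap does not originate in the SAP. It lies inside the protocol, between 5.3 on one side and 11.3.7 and 8.13 on the other. The odds ratio and interval were already planned in 11.3.7; the SAP adds the ordinal model and the p-value. This explains the omission, but an analysis section that is silent does not override an explicit endpoint definition. Nor does objective 4.3 settle the matter: it speaks of previous psoriasis treatments in general, so its non-naïve group need not be the group in 5.3.

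A reader might infer that including naïve subjects dilutes the comparison towards no difference. The documents do not support that. Dilution needs naïve subjects to be present, to answer, and to show a smaller difference between arms than previous users. None of the three is documented, and other patterns leave the estimate unchanged or inflate it.

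**Conclusion.** The mismatch stands: 5.3 restricts both endpoints to previous users of topical treatment, while SAP 6.6.4 and Tables E18 and E19 name all randomised subjects and declare no change. The odds ratios, intervals and p-values may therefore describe a population other than the one in the endpoint definition, and may include answers without a referent.

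The distortion cannot be sized from the documents. The span of 1.62 to 2.44 around an assumed 2.0 is illustrative, rests on the assumed distribution, naïve share and answer patterns, and applies to the time item only. Zero distortion is within the range.

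The consequence is limited. Both endpoints are exploratory, and the primary, secondary and safety analyses are untouched. It is still worth correcting, because the wording change is small and these results bear directly on the rationale for the foam.

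**What to change.** In SAP 6.6.4 and in the titles of Tables E18 and E19, set the population to full analysis set subjects with previous topical treatment for psoriasis, citing protocol 5.3. State which recorded data identify previous use, and report the number of naïve subjects excluded in each arm. A version in all full analysis set subjects should be supportive at most, and labelled as such.

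The cost is a somewhat smaller n and some work on the flag. Protocol 8.3, 8.3.1 and 8.4 list diagnoses, medical and surgical history, and concurrent medication and procedures, but no explicit item for previous topical psoriasis treatment. The SAP must therefore say how the flag is derived, for instance whether medication records are sufficient, and what happens to subjects who cannot be classified.

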6.7 Analysis of Safety

The analysis of safety will be based on the safety analysis set as described in the CTP (section 11.3.8).

6.7.1 Exposure

In addition to what is stated in the CTP (section 11.3.3), the number of days of exposure will be calculated as the date of final application minus the date of first application plus 1,

ignoring any interim missing applications. The duration of exposure to treatment (weeks) will be derived as the number of days of exposure divided by 7, and will be summarized for each treatment group using the mean, SD, median, minimum and maximum values. The sum of duration of exposures to treatment will be presented as all subjects-treatment-weeks.

6.7.2 Adverse Events

AEs will be analysed as described in the CTP (section 11.3.8.1), with the following additions and clarifications.

Three tables will be produced counting AEs by each causal relationship; not related, possibly related and probably related, respectively.

If different categories of causal relationship were observed for the same SOC and preferred term in one subject, count as one event for each causal relationship.

In addition, three causal relationships will be divided into two categories; "not related" and "related" (possibly related and probably related), and a table for "related" events will be presented. If several events are observed for the same SOC and preferred term in one subject, count as one event for the greatest causality.

Separate tables for "lesional/perilesional" and "distant" cutaneous AEs will also be produced.

Adverse drug reactions are defined as adverse event that is related to trial medication:

Adverse event that is related to trial medication are those classified as the probable or possible relationship to trial medication.

6.7.3 Laboratory Data

The analysis of laboratory parameters will be performed as outlined in the CTP (section 11.3.8.2).

In principle, the value measured at Visit 1 is used as baseline. If the value is missing at Visit 1 but there is a measurement prior to first application of trial medication, then this measurement will be considered as the baseline value for laboratory safety examinations.

6.8 General Principles

6.8.1 Handling of Drop-outs and Missing Values

A LOCF approach will be used to impute missing values at Visit 4 (end of week 4) for the primary endpoint as described in the CTP (section 11.3.11).

LOCF will be used to impute missing values for the analysis of change from baseline to Visit 4 (end of week 4) in the sum of total sign score and the analysis of change from baseline to Visit 4 (end of week 4) in change in score for the severity of each clinical sign.

